3.6 POST-TREATMENT EVALUATIONS

Post treatment evaluations (i.e., End of Treatment Visit) will be performed approximately 30 days after the last dose of protocol treatment. If a subject initiates a new anti-cancer therapy within 30 days after the last dose of trial treatment, the 30-day safety follow-up visit must occur before the first dose of the new therapy. If the patient cannot return to the Clinical Center for this visit, a request will be made to have a local physician or laboratory collect a CBC with differential and send the results. If this is not possible, patients may be assessed by telephone for symptoms.

Unless otherwise noted, follow-up will occur at the following time point: every 60 days (\pm 7 days) for 6 months; then every 90 days (\pm 14 days) for 2 years; then every six months (\pm 28 days) for 2 years, then annually (\pm 6 weeks) at the discretion of the investigator. Any other evaluations and tests should be performed as clinically indicated.

Upon disease progression or initiation of other anti-cancer therapy, contact will be for survival only until the subject is off study (i.e., every 3 months [\pm 4 weeks]); unless otherwise clinically indicated. See Study Calendar (Section [3.7](#)) for additional information. Any adverse events which are present at the time of discontinuation should be followed in accordance with the safety requirements.

Patients who stop treatment early will be followed until completion of the Safety Follow-up Visit or until death, whichever occurs first. Patients removed from study treatment for unacceptable adverse event(s) will be followed until resolution or stabilization of the adverse event.

Abbreviated Title: IL-15+Mogamulizumab

Version Date: 11/16/2020

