3.6.1 Safety Follow-Up Visit

The safety follow-up visit should occur 30 days (± 7 days) after the last dose of trial treatment, or before the initiation of a new anti-cancer treatment, whichever comes first. Required testing is as noted in the Study Calendars (Section 3.7) All AEs that occur prior to the Safety Follow-Up Visit should be recorded. Patients with an ongoing, treatment-related AE of Grade > 1 will be followed until the resolution of the AE to Grade 0-1, stabilization of the AE in the opinion of the investigator, or until the beginning of a new anti-neoplastic therapy, whichever occurs first. SAEs that occur within 30 days of the end of treatment or before initiation of a new anti-cancer treatment should also be followed and recorded.

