3.6.2 Follow-Up Visits — Prior to Disease Progression

Patients who complete trial treatment without evidence of disease progression will move into the Follow-up Phase and may be assessed every 60 days (± 7 days) for 6 months; then every 90 days (± 14 days) for 2 years; then every six months (± 28 days) for 2 years, then annually (± 6 weeks) after finishing treatment by radiologic imaging or other clinical assessments to monitor disease status. Every effort should be made to collect information regarding disease status until the start of new anti-neoplastic therapy, or disease progression. If the patient cannot return to the Clinical Center for any of these visits, a request will be made to have a local physician or laboratory collect a CBC with differential and send the results. If this is not possible, patients may be assessed by telephone or email for symptoms.

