3.6.3 Follow-Up Visits — Survival/Post-Disease Progression

Once a subject experiences confirmed disease progression or starts a new anti-cancer therapy, the subject moves into the survival follow-up phase and should be contacted (e.g., phone, email, etc.; in-person visit not required) at least every 6 months (± 4 weeks) to collect information on new anti-cancer treatments received and to assess for survival status until death, withdrawal of consent, or the end of the study, whichever occurs first (see Study Calendar)

Abbreviated Title: IL-15+Mogamulizumab
Version Date: 11/16/2020

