Tissue immune cell subsets	• Two core biopsy samples in RPMI 1640 with 10% human serum and antibiotics • One core biopsy sample in formalin NOTE: Samples may be tumor tissue or bone marrow aspirate/biopsy	X**		(X)			(X)	[name] (Laboratory of Pathology)
Single-cell RNA-Seq	• One core biopsy sample in RPMI 1640 with 10% human serum and antibiotics	(X)		(X)				[name] (Laboratory of Pathology) and CCR single cell core
Other Samples								
Germline DNA	• Blood, Buccal Swab, or Saliva (preferred)	X						[name] (Leidos CSL)

Abbreviated Title: IL-15+Mogamulizumab

Version Date: 11/16/2020

Sample	Collection Details*	Time Points						Supervising Laboratory/ Investigator		
		Baseline	C1 D8	C1 D15	C2-6 D1	C2-6 D15	Follow-up [#]			
(X) = Optional; samples will be collected if adequate time/staff available for processing. If an optional sample is not collected at baseline, it would also not be collected in follow-up unless specifically requested by the PI.										
*Tubes/media may be adjusted at the time of collection based upon materials available or to ensure the best samples are collected for planned analyses.										
** Tumor biopsy is required if archival tissue is not available or adequate; otherwise, this is optional										
#Subjects who discontinue treatment for a reason other than disease progression and who do not start new treatment should continue to have study bloods collected at the scheduled time points.										
¹ At the end of treatment only.										
² For ADCC of mogamulizumab, Baseline and C1D8 samples should be collected for at least one patient per dose level, and for at least three patients at the MTD										
³ At each follow-up visit prior to disease progression, as specified in Section 3.6.2 .										

Note: If there is an optional biopsy for research in the protocol, then the patient will consent at the time of the procedure. If the patient refuses the optional biopsy at that time, the refusal will be documented in the medical record and in the research record.

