10.4.3 Analysis of the Secondary Endpoints

The duration of response (DOR; beginning at the date clinical response is first identified), overall survival (OS), event free survival (EFS), and progression free survival (PFS) will be estimated using Kaplan-Meier curves with appropriate confidence intervals reported.

Every report of response rates and time to progression should contain all patients included in the study. For the response calculation, the report should contain at least a section with all eligible patients. Another section of the report may detail the response rate for evaluable patients only. However, a response rate analysis based on a subset of patients must explain which patients were excluded and for which reasons. 95% confidence limits will be given.

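### Section 3.6 ends follow-up of early stoppers at the safety visit, in conflict with 3.6.3 and other sections; applied literally it would truncate OS after early progression and leave later PFS and EFS events unobserved

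*Combined protocol and SAP*

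**What the plan says.** Section 3.6 contains the sentence at issue: "Patients who stop treatment early will be followed until completion of the Safety Follow-up Visit or until death, whichever occurs first". Section 3.6.1 fixes the timing: "The safety follow-up visit should occur 30 days" after the last dose, with a 7-day window, or before a new anti-cancer treatment if that comes first.

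Other places describe follow-up differently:

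- **Section 3.6, general schedule:** "Unless otherwise noted, follow-up will occur at the following time point: every 60 days", then at widening intervals.
- **Section 3.6, survival contact:** "Upon disease progression or initiation of other anti-cancer therapy, contact will be for survival only until the subject is off study", at 3-month intervals.
- **Section 3.6.2:** "Patients who complete trial treatment without evidence of disease progression will move into the Follow-up Phase". Patients who stop early are not mentioned.
- **Section 3.6.3:** any subject with confirmed progression or new therapy is contacted at least every 6 months to "assess for survival status until death, withdrawal of consent, or the end of the study, whichever occurs first".
- **Section 3.7, calendar footnotes 6 and 7:** disease follow-up runs to progression or new therapy, then survival contact about every 6 months. Early stoppers are not excluded.
- **Section 3.9 and 3.9.2:** follow-up after removal from therapy continues as in 3.6, and early stopping is not an off-study criterion.
- **Section 5.1, table footnote on research bloods:** "Subjects who discontinue treatment for a reason other than disease progression and who do not start new treatment should continue" to give samples at the scheduled times.

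Section 10.4.3 says that DOR, OS, EFS and PFS "will be estimated using Kaplan-Meier curves with appropriate confidence intervals reported". Sections 6.3.6 to 6.3.8 define PFS, OS and EFS without a censoring rule.

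**The concern.** Progression or new therapy before the end of cycle 6 is itself an early stop. For those patients the sentence in 3.6 and the survival follow-up in 3.6.3 cannot both be followed. For patients who stop for toxicity, refusal or investigator decision, without progression or new therapy, 3.6.2 does not clearly apply.

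Kaplan-Meier estimation assumes that censored patients have the same later risk as those still under observation. Censoring OS a month after progression breaks that assumption, because progression predicts death. Ending disease assessment a month after a stop without progression loses events, and it biases PFS if the later risk of these patients differs from that of the others. With at most 18 evaluable patients, events that were never collected cannot be recovered at analysis.

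**Working it through.** The plan gives no figure for follow-up, rate of early stopping or precision of the time-to-event endpoints, so there is none to reproduce on this point. Section 10.2 gives only escalation probabilities and the evaluable sample size (6 + 12 = 18 at most, 3 + 12 = 15 at least).

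**Inputs from the protocol.** Six cycles of 28 days: 168 / 30.44 = 5.5 months. Single-agent mogamulizumab in ATLL (1.2.1.1): median PFS 5.2 and median OS 13.7 months. Single-agent mogamulizumab in cutaneous T-cell lymphoma (1.2.2.1): median PFS 7.7 months. These are historical values, used only for illustration.

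**Step 1. Share progressing before treatment ends (exponential assumption).** P = 1 - 2^(-5.52 / median).

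- Median 5.2 months: 1 - 2^(-1.061) = 0.52.
- Median 7.7 months: 1 - 2^(-0.717) = 0.39.

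**Step 2. OS under the literal reading, ATLL inputs.** Assume exponential time to progression with rate a = ln 2 / 5.2 = 0.1333 per month, then exponential survival after progression with rate b. Overall survival is S(t) = (a·e^(-bt) - b·e^(-at)) / (a - b). Setting S(13.7) = 0.5 gives b = 0.1130, a median of 6.1 months after progression. Patients progressing before 5.52 months are censored 30 days later. The chance that their death is seen is 1 - e^(-0.1130 × 30/30.44) = 0.105. Kaplan-Meier on 400,000 simulated patients, which shows bias and not sampling error, gives:

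| | Full follow-up | Literal reading |
|---|---|---|
| Median OS, months | 13.7 | 18.2 |
| 12-month OS | 57% | 75% |
| Death observed by 24 months | 79% | 37% |

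For 12 patients at the MTD, the last row is 0.79 × 12 = 9.5 against 0.37 × 12 = 4.4 deaths. The model has no deaths without progression. No OS figure is computed for MF/SS, because the protocol gives no median OS for mogamulizumab in that disease.

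**Step 3. PFS in patients who stop without progression.** The documents give no stop rate and no later hazard, so both are assumed. A share of 20% or 40% of patients is given a stop time uniform over months 1 to 4, which counts only if progression has not come first (about 14% and 29% of patients at median 5.2 months). After the stop the progression hazard is multiplied by a ratio, and the patient is censored 30 days later. The entries are literal minus full follow-up, in percentage points of 6-month PFS:

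| Hazard ratio after stop | 20%, median 5.2 | 40%, median 5.2 | 20%, median 7.7 | 40%, median 7.7 |
|---|---|---|---|---|
| 0.5 | -1.7 | -3.3 | -1.4 | -2.6 |
| 1 | about 0 | about 0 | about 0 | about 0 |
| 2 | +2.1 | +4.0 | +2.1 | +3.9 |
| 3 | +3.2 | +6.0 | +3.3 | +6.4 |

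At median 5.2 months and hazard ratios 1 to 3, PFS events observed in 18 patients fall from about 17 to about 13 to 16. This loss occurs even where the bias is zero.

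**Step 4. Which endpoint is touched, and for whom.**

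- Stop for progression: the PFS, EFS and DOR event has already been recorded. Only OS can be cut.
- Stop without progression or new therapy: later PFS and EFS events, ATLL DOR events and deaths can be missed.
- New lymphoma therapy while still under observation is an EFS event (6.3.8), not a censoring.
- MF/SS TTP and DOR: 6.3.2 already uses the off-treatment date, so this sentence does not determine them.
- MTD and DLT: these are judged in the first 28 days and are unaffected.

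**The case against.** The strongest answer is that most of the protocol points to continued follow-up: the general schedule and survival contact in 3.6, Section 3.6.3, the calendar footnotes, 3.9, 3.9.2 and the footnote in 5.1. The sentence after the disputed one says that patients removed for unacceptable adverse events are followed until the event resolves or stabilises. The disputed sentence could therefore be a minimum for safety follow-up. A site reading it that way would lose nothing.

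Much of this stands. A reader might infer that early stoppers will in fact be lost at 30 days and that PFS, EFS, DOR and OS are all biased upward. The documents do not support that. The sentence is one of two conflicting instructions, the endpoints are affected differently, and the direction of any PFS bias is an assumption. Even 6 points is small beside sampling error: at n = 18 and 6-month PFS of 45%, the 95% half-width is 1.96 × √(0.45 × 0.55 / 18) = 23 points. The 52% applies to the ATLL median only, and the trial also enrols MF/SS.

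The contradiction remains. The general schedule in 3.6 gives way where something else is noted, and the disputed sentence can be read as such a note. Section 3.9 only refers back to 3.6. Adverse-event follow-up is not disease assessment. Section 3.6.2 names only patients who complete treatment.

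**Conclusion.** The conflict is real and should be resolved. The largest exposure is OS: under the literal reading, follow-up would end about a month after stopping for the 39% to 52% of patients expected to progress before the end of cycle 6. This censoring is informative and would overstate OS, by about 4.5 months at the median with the ATLL inputs (18.2 - 13.7). The second exposure is narrower: unobserved PFS and EFS events, and ATLL DOR events, in patients who stop without progression or new therapy. The resulting shift in 6-month PFS is about -3 to +6 points for 20% to 40% stopping and hazard ratios of 0.5 to 3, and zero if the hazard does not change.

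These sizes rest on exponential times, single-agent historical medians and assumed stop rates, and they arise only if the sentence is applied as written. The affected endpoints are secondary. Dose finding, the DLT assessment and the sample size are untouched.

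**What to change.** Reconcile the passages by amendment:

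1. In 3.6, limit the sentence to safety follow-up.
2. In 3.6.2, widen entry to patients who complete or stop trial treatment without progression, so that they follow the existing schedule until progression or new therapy.
3. State that patients with progression or new therapy enter 3.6.3 whatever their reason for stopping treatment.
4. Reconcile the survival contact interval, which is 3 months in 3.6 but 6 months in 3.6.3 and the calendar.

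The cost is a short amendment and already scheduled follow-up visits for a few more patients. No treatment rule changes.

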3.6.1 Safety Follow-Up Visit

The safety follow-up visit should occur 30 days (± 7 days) after the last dose of trial treatment, or before the initiation of a new anti-cancer treatment, whichever comes first. Required testing is as noted in the Study Calendars (Section 3.7) All AEs that occur prior to the Safety Follow-Up Visit should be recorded. Patients with an ongoing, treatment-related AE of Grade > 1 will be followed until the resolution of the AE to Grade 0-1, stabilization of the AE in the opinion of the investigator, or until the beginning of a new anti-neoplastic therapy, whichever occurs first. SAEs that occur within 30 days of the end of treatment or before initiation of a new anti-cancer treatment should also be followed and recorded.

3.6.2 Follow-Up Visits — Prior to Disease Progression

Patients who complete trial treatment without evidence of disease progression will move into the Follow-up Phase and may be assessed every 60 days (± 7 days) for 6 months; then every 90 days (± 14 days) for 2 years; then every six months (± 28 days) for 2 years, then annually (± 6 weeks) after finishing treatment by radiologic imaging or other clinical assessments to monitor disease status. Every effort should be made to collect information regarding disease status until the start of new anti-neoplastic therapy, or disease progression. If the patient cannot return to the Clinical Center for any of these visits, a request will be made to have a local physician or laboratory collect a CBC with differential and send the results. If this is not possible, patients may be assessed by telephone or email for symptoms.

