6.3.2 Response Criteria for MF/SS

Global Response (GR) score (**APPENDIX C**) will be used for assessing response in patients with CTCL ([41](#)). GR score incorporates separate responses in each component of the TNBM staging (i.e., skin, nodes, viscera and blood; **APPENDIX C**). No patient with a global OR should have less than a PR in the skin.

Abbreviated Title: IL-15+Mogamulizumab

Version Date: 11/16/2020

The mSWAT ([19](#)) is an instrument utilized to track the skin tumor burden in MF/SS. It measures the percentage total body-surface area (TBSA, %) involvement separately for patches, plaques, and tumors within 12 body regions using the patient's palm and fingers representing 1% of TBSA. Patients with erythroderma are assessed for percentage of TBSA involved with patches and/or plaques. The percentage of TBSA for each lesion type is multiplied by a number (patch = 1, plaque = 2; tumor = 4) and summed to derive the mSWAT score. The mSWAT for each patient will be determined by the same individual at all study visits.

A complete response (CR) requires 100% clearing of skin disease and a partial response (PR) requires $\geq 50\%$ reduction in the mSWAT score compared with baseline. CR/PR requires confirmation by repeat assessment after ≥ 4 weeks. Stable disease is defined as less than 50% reduction to less than 25% increase in the mSWAT score compared with baseline. PD is defined as $\geq 25\%$ increase in the mSWAT score from baseline or $\geq 50\%$ increase in the sum of the products of the greatest diameters of pathologically positive lymph nodes compared with baseline.

Time to response is the time from the first treatment dose until the patient first meets the criteria for a 50% decrease in the GR score. The duration of response (DOR) is the time from first CR/PR until the GR score is increased from nadir to more than 50% of the difference between the baseline and nadir scores. Time to progression (TTP) is the time from start of treatment until PD. If patients goes off treatment for any purpose, this date is used for determination of TTP and/or DOR.

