6.3.5 Duration of Response

The duration of response (DOR) is measured from the time measurement criteria are met for CR or PR (whichever is recorded first) until the first date that recurrent or progressive disease is objectively documented (taking as reference for progressive disease the smallest measurements recorded since the treatment started), death, or, in the absence of PD, date of last assessment.

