6.3.6 Progression-Free Survival

Progression-free survival (PFS) is defined as the duration of time from the date of study enrollment until time of disease relapse, disease progression, or death, whichever occurs first.

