6.3.9 Duration of Response

Duration of overall response: The duration of overall response is measured from the time measurement criteria are met for CR or PR (whichever is first recorded) until the first date that

Abbreviated Title: IL-15+Mogamulizumab

Version Date: 11/16/2020

recurrent or progressive disease is objectively documented (taking as reference for progressive disease the smallest measurements recorded since the treatment started).

The duration of overall CR is measured from the time measurement criteria are first met for CR until the first date that progressive disease is objectively documented.

Duration of stable disease: Stable disease is measured from the start of the treatment until the criteria for progression are met, taking as reference the smallest measurements recorded since the treatment started, including the baseline measurements.

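### PFS and TTP start on different dates, PFS runs past new therapy when only survival is followed, and the end rules for MF/SS TTP and for DOR conflict

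*Combined protocol and SAP*

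**What the plan says.** **Origins.** Section 6.3.6 measures PFS "from the date of study enrollment until time of disease relapse, disease progression, or death, whichever occurs first". EFS and OS (Sections 6.3.8 and 6.3.7) also start at enrolment. Section 6.3.2 has a different origin: "Time to progression (TTP) is the time from start of treatment until PD". That is the only definition of TTP, and it sits in the MF/SS section, although Section 1.1.2 makes TTP an objective for ATLL too.

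**New therapy.** Section 6.3.8 makes alternative lymphoma therapy an event for EFS. Section 6.3.6 does not mention it for PFS. Section 3.6 says that after progression or other anti-cancer therapy "contact will be for survival only until the subject is off study", and Section 3.6.3 agrees. Sections 10.4.1 and 10.4.3 give Kaplan-Meier estimation without a censoring rule.

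**Off-treatment date.** Section 6.3.2 continues: "If patients goes off treatment for any purpose, this date is used for determination of TTP and/or DOR". It does not say whether that date is an event or a censoring time.

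**DOR.** There are three definitions.
- Section 6.3.2 (MF/SS) ends DOR on a rise in the global response score or at the off-treatment date.
- Section 6.3.5 ends it at documented recurrence or progression, "death, or, in the absence of PD, date of last assessment".
- Section 6.3.9 begins "The duration of overall response is measured from the time measurement criteria are met for CR or PR" and ends only at documented progression or recurrence.

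**Fallback contacts.** Section 3.6.2 plans imaging or other clinical assessment at follow-up visits. If the patient cannot return, a local CBC is requested; failing that, "If this is not possible, patients may be assessed by telephone or email for symptoms".

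**The concern.** A progression is an event for both PFS and TTP. With a common origin, PFS can therefore never exceed TTP in the same patient. Here it can, because of the origins and because of the off-treatment sentence.

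Once new therapy starts without progression, the plan stops looking for progression but leaves the PFS clock running. For those patients death is the only event still collected systematically, so PFS turns into survival time.

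The trial has one arm, so a reader is likely to set its PFS against the single-agent mogamulizumab medians quoted in the background. Section 10.4.7 then splits every secondary endpoint by diagnosis and CCR4 status. As written, two analysts could derive different PFS, TTP and DOR from the same records.

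**Working it through.** The plan states no event count, precision or power for PFS, TTP or DOR, so it has no figure of its own to reproduce on this point. The check is date arithmetic plus an illustrative simulation.

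**Inputs from the documents**
- Median PFS 5.2 and OS 13.7 months in ATLL (Section 1.2.1.1); median PFS 7.7 months in MF/SS (Section 1.2.2.1), all single-agent mogamulizumab.
- At most 6 cycles of 28 days (précis, Section 3.1).
- Disease evaluation every 8 weeks on treatment (Section 3.7), then every 60 days, 90 days and six months (Section 3.6.2).
- No maximum gap from enrolment to first dose is stated. I assume 7 to 28 days; the upper end borrows the baseline-test window in Section 2.4.

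**1. Origin.** For one progression date, PFS minus TTP equals the gap. With 30.4375 days per month:
- 7 days: 7/30.4375 = 0.23 months, which is 4.4% of 5.2 or 3.0% of 7.7.
- 28 days: 28/30.4375 = 0.92 months, which is 17.7% of 5.2 or 11.9% of 7.7.

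**2. PFS past new therapy.** The simulation used 20,000 patients, exponential PFS and the visit schedule above. Assumptions:
- 0, 15 or 30% of patients start new therapy without documented progression, at a time uniform over days 28 to 168 and unrelated to prognosis.
- 0, 25 or 50% of post-treatment visits are replaced by phone or CBC.
- Median survival afterwards is 8.5 months in ATLL (13.7 − 5.2) and 12 months in MF/SS (assumed).

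Reading A follows the PFS text literally. Reading B censors at the last disease assessment before new therapy, and also when progression is found after two or more missed assessments.

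| True median (true 12-month PFS) | New therapy | A | B | A − B |
|---|---|---|---|---|
| 5.2 months (0.20) | 0% | 0.22–0.29 | 0.22–0.27 | 0–0.02 |
| 5.2 months (0.20) | 30% | 0.32–0.36 | 0.22–0.27 | 0.09–0.10 |
| 7.7 months (0.34) | 0% | 0.36–0.43 | 0.36–0.42 | 0–0.01 |
| 7.7 months (0.34) | 30% | 0.46–0.51 | 0.36–0.42 | 0.09–0.10 |

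Ranges run over the share of replaced visits. At 15% new therapy, A − B is about 0.05. The remaining distance from B to the true value comes from visit spacing and missed visits, which a censoring rule does not recover.

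**3. Off-treatment date in MF/SS.** Section 3.9.1 lists completion of up to 6 cycles as a reason for leaving protocol therapy, so completers are covered by the sentence as worded.
- Cap: 6 × 28 = 168 days = 5.5 months, apart from cycle delays. This is below the cited 7.7-month median.
- Share without progression at day 168, exponential: 0.5^(5.52/7.7) = 0.61.
- If the date is an event, those 61% end together and median TTP sits at about 5.5 months. If it is censoring, the curve stops near 0.61 and the median is not reached.
- A response first recorded at the 8-week evaluation (day 56) has a DOR of at most 168 − 56 = 112 days, about 3.7 months.

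PFS continues past day 168, so for these patients TTP falls below PFS by far more than the origin gap.

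**The case against.** **These are secondary, descriptive endpoints in a phase 1 trial.** There are at most 18 evaluable patients and no hypothesis test. At 12-month PFS of 0.20 and n = 18, the simple standard error is √(0.2 × 0.8/18) = 0.09, about the size of the largest rule-related bias. That limits the importance. It does not justify conflicting definitions.

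**Counting events after new therapy is a recognised PFS convention, and EFS already treats new therapy as an event.** Both are true. But the convention depends on continued disease assessment, which this plan ends at that point. Censoring has its own cost if patients who switch differ in prognosis, which is a reason to report EFS beside it.

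**A reader might infer that phone or CBC contacts are credited as progression-free time.** No section says so. Section 3.6.2 separates symptom checks from disease monitoring, and the last assessment in Section 6.3.5 reads naturally as a disease assessment. With no new therapy, the censoring rule changes 12-month PFS by at most 0.02. Nor is a CBC worthless: blood progression in ATLL (Section 6.3.3) rests on flower cells and the absolute lymphocyte count. It cannot exclude progression elsewhere.

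**A reader might infer that DOR is overstated.** In MF/SS the off-treatment sentence shortens it. Under Section 6.3.5 it would be lengthened only if a phone or CBC contact counted as an assessment. Section 6.3.9 gives no censoring date.

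**Larger effects can be produced.** If half or all of those progression-free at 6 months switched, 12-month PFS in ATLL would read 0.27 or 0.33 instead of 0.20. No document supports those rates, and the calculation uses the full 13.7-month OS as survival from month 6. Setting the origin gap against the 2.0-month median in Section 1.2.1.1 gives up to 46%, but that median belongs to alemtuzumab.

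**Conclusion.** The point holds in limited form.
- **Established by the text:** PFS and TTP have different origins; PFS has no stop at new therapy while disease follow-up does; DOR has three incompatible definitions; and the MF/SS off-treatment rule is the larger reason TTP can fall below PFS.
- **Size, conditional on assumptions:** 0.23 to 0.92 months for a 7 to 28 day gap, at most about 12% of a 7.7-month or 18% of a 5.2-month median; and about 0 to 0.10 in 12-month PFS for 0 to 30% new therapy without progression.
- **Direction:** PFS can be overstated. MF/SS TTP and DOR can be cut short. A general overstatement of DOR is not supported.

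The MTD and the escalation rules are unaffected. The point should be corrected before the efficacy endpoints are analysed.

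**What to change.** In Sections 6.3 and 10.4.3:
1. Start PFS, EFS, OS and TTP at first dose.
2. Censor PFS, TTP and DOR at the last Section 6.3 disease assessment before new anti-cancer therapy. Name EFS, where new therapy is an event, as the sensitivity analysis.
3. State that a phone, email or CBC-only contact is not a disease assessment that extends progression-free time, but that a CBC meeting the blood progression criterion still counts as progression.
4. Use one TTP and one DOR definition for both diseases, and remove the off-treatment date as an endpoint.

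The cost is a protocol wording amendment, which needs IRB approval under the Statement of Compliance, with no new visits or patients. PFS estimates become slightly shorter, and some censoring will be informative if patients who switch differ in prognosis.
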